- Patient's satisfaction with the treatment process
- Pain assessment during the injection using a 11-point visual analogue scale
- Safety assessment of Embella® injectable solution

Study Method

It was a single group, before and after the clinical study. The study protocol as well as other essential documents (such as CRF, ICF, etc.) were approved by the Undersecretary of Research, Tehran University of Medical Sciences .

Also, all mentioned documents were approved by the ethics committee of Tehran University of Medical Sciences on 17 January 2023 (code: IR.TUMS.TIPS.REC.1401.102). The protocol was registered in the Iranian Registry of Clinical Trial Registry (IRCT) with registration number IRCT20190210042676N29.

Inclusion Criteria

- Age between 18 and 65 years old
- Individuals with any severity of unwanted submental fat
- Voluntarily signed the informed consent form and consented to the 3-month follow-up
- Willing to actively participate in the study and the scheduled visits

Exclusion Criteria

- Any previous interventions to treat SMF
- Anatomical features or previous trauma in the injection site which is liable to interfere with SMF evaluation or result in an aesthetically unacceptable outcome after treatment
- Evidence of any cause of submental enlargement other than SMF
- Patients with a body mass index (BMI) $> 30 \text{ kg m}^2$
- Those undergoing or considering a weight-reduction program
- Patients with a history of sensitivity to any components of the study medication or topical or local anesthetics
- Patients with a history of dysphagia
- Any inflammation, active infection, unhealed wound, or tissue scar at injection site
- Those using anticoagulants or NSAID or other medications that increase the risk of coagulation disorders within 7 days before injection
- Unrealistic expectations
- Pregnant or lactating women
- Those undergoing low sodium diets like hypertensive patients

Intervention

- Minimum 1 and maximum 3 treatment sessions (with at least 4 weeks intervals) with 2 ml of Embella® injectable solution, which contains 20 mg of DCA.
- 4 weeks after the first and second injections, the patient will be evaluated by the physician and research team. If necessary, they will receive additional injections; otherwise, they will proceed with post-injection follow-up.

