Primary and secondary endpoints are evaluated before injection and 4 and 12 weeks after the last injection.

Primary Endpoint

At least one-grade improvement in standard grading of submental fat (SMF) evaluated at 4 and 12 weeks after the last injection (Figure 4)

Figure 4: Standard grading of submental fat (SMF)

| Scale | 0 | 1 | 2 | 3 | 4 |
|----------------------------|---|---|--|---|---|
| Submental Convexity | Absent | Mild | Moderate | Severe | Extreme |
| Description | No localized submental fat evident | Minimal localized submental fat | Prominent localized submental fat | Marked localized submental fat | Extreme submental convexity |
| Representative Photographs |  |  |  |  |  |
| |  |  |  |  |  |
| |  |  |  |  |  |

Secondary Endpoints

- Submental fat diameter will be measured with the calliper at 4 and 12 weeks after the last injection
- Intensity of procedural pain will be assessed using the Visual Analogue Scale (VAS), ranges from 0 (complete painlessness) to 10 (maximum pain).
- Patient satisfaction will be assessed using the Visual Analogue Scale (VAS), ranges from 0 (not satisfied at all) to 10 (maximum satisfaction).
- Any observed or reported adverse events will be recorded after the injections and at 4 and 12 weeks follow-up visits, graded as mild [1] moderate [2] and severe [3].

Study Timeline

| Visit No | 0 | 1 | 2 | 3 | 4 | 5 | 6 |
|--|----------|-------------|---|---|------------------------|---|---|
| | Day 1 | | | | | | |
| Time | Baseline | Injection 1 | Week 4 (± 2 days) (Injection 2)/ Follow-up of subjects with a satisfactory response who do not require further treatment | Week 8 (± 4 days) (Injection 3)/ Follow-up of subjects with a satisfactory response who do not require further treatment | Week 12 ± 4 day | Week 16 ± 4 day (In subjects with 2 injections) | Week 20 ± 4 day (In subjects with 3 injections) |
| Screening | X | | | | | | |
| eligibility control | X | | | | | | |
| Consent | X | | | | | | |
| Demographic data | X | | | | | | |
| Injection | | X | X | X | | | |
| Pain assessment | | X | X | X | | | |
| Digital Photography | X | | X | X | X | X | X |
| Measurement of submental fat | X | | X | X | X | X | X |
| Patients' satisfaction | | | X | X | X | X | X |
| Physicians' assessment According to SMF | X | | X | X | X | X | X |
| Adverse Events | X | X | X | X | X | X | X |

Study Visits:

Visit 0: Screening & eligibility control

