The following screening procedures will be conducted to determine eligibility: The investigator will evaluate each patient against the inclusion and exclusion criteria. If the patient is eligible to participate in the study, the study process will be explained to them in an understandable and verbal manner, and a consent form will be provided. Once the information presented to the patient has been thoroughly reviewed and understood by them, and they have received the necessary explanations, the patient will be asked to write their full name on the consent form and sign it. Following the completion of these steps, the following actions will be carried out:

- Digital AP and lateral photography of the patient's neck
- Grading of submental fat based on SMF
- Measurement of submental fat diameter

Visit 1 (day 1):

- Solution injection by the physician
- Monitor the patient for up to half an hour after injection
- Reporting and recording adverse events
- Pain assessment

Visit 2 (4 weeks±2 days):

In case of complete recovery with the physician's opinion:

- Digital AP and lateral photography of the patient's neck
- Grading of submental fat based on SMF
- Measurement of submental fat diameter
- Reporting and recording adverse events
- Evaluation the patient satisfaction

If re-injection is needed:

- Solution injection by the physician
- Monitor the patient for up to half an hour after injection
- Digital AP and lateral photography of the patient's neck
- Pain assessment
- Reporting and recording adverse events

Visit 3 (8 weeks±4 days):

In case of complete recovery with the physician's opinion:

- Digital AP and lateral photography of the patient's neck
- Grading of submental fat based on SMF
- Measurement of submental fat diameter
- Reporting and recording adverse events
- Evaluation the patient satisfaction

If re-injection is needed:

- Solution injection by the physician
- Monitor the patient for up to half an hour after injection
- Digital AP and lateral photography of the patient's neck
- Pain assessment
- Reporting and recording adverse events

Visit 4 (12 weeks±4 days):

- Digital AP and lateral photography of the patient's neck
- Grading of submental fat based on SMF
- Measurement of submental fat diameter
- Reporting and recording adverse events
- Evaluation the patient satisfaction

Visit 5 (16 weeks±4 days) (In subjectswith 2 injections):

- Digital AP and lateral photography of the patient's neck
- Grading of submental fat based on SMF

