STATISTICAL

ANALYSIS PLAN

Safety and efficacy assessment of deoxycholic acid (Embella[®]) injectable solution for the reduction of unwanted submental fat

NCT Number: NCT06509438

Date: November 20, 2022

STATISTICAL ANALYSIS PLAN

Name of Test Drug:	Embella®
Methodology:	Interventional, single-armed
Sponsor:	Espad Pharmed Darou Company
	Office:
	Espad Pharmed, [name]
	[contact]
Sponsor Representatives:	Zist Orchid Pharmed Co.
Statistical Analysis Plan Date:	November 20, 2022
Statistical Analysis Plan Version:	Version 1.0

Contents

Participate timeline	4
Section 1: Administrative information	5
Title and Trial registration.....	5
Trial registration number	5
SAP Version (SAP version number with dates)	5
Section 2: Introduction	5
Objectives.....	5
Primary objective(s):	5
Secondary objective(s):	5
Section 3: Trial Methods	5
Trial design – description of trial design	5
Inclusion Criteria	6
Exclusion Criteria	6
Withdrawal of Subjects	6
Randomization.....	7
Sample size	7
Section 4: Outcome Variables	7
Endpoints.....	7
Primary Endpoint.....	7
Secondary Endpoints	8
Safety End point	8
Section 5: Statistical analysis	10
Patient Characteristics and Baseline Comparisons.....	10
Primary and Secondary Endpoint Analysis	10
Safety Analysis.....	10
List and describe each primary and secondary outcome including details of: methods used for assumptions to	

be checked for statistical methods.....	11
Missing Data.....	11
Covariate Adjustment.....	11
Statistical Software.....	11

Participate timeline

Visit No	0	1	2	3	4	5	6
	Day 1						
Time	Baseline	Injection 1	Week 4 (± 2 days) (Injection 2)/ Follow-up of subjects with a satisfactory response who do not require further treatment	Week 8 (± 4 days) (Injection 3)/ Follow-up of subjects with a satisfactory response who do not require further treatment	Week 12 ± 4 day	Week 16 ± 4 day (In subjects with 2 injections)	Week 20 ± 4 day (In subjects with 3 injections)
Screening	X						
eligibility control	X						
Consent	X						
Demographic data	X						
Injection		X	X	X			
Pain assessment		X	X	X			
Digital Photography	X		X	X	X	X	X
Measurement of submental fat	X		X	X	X	X	X
Patients' satisfaction			X	X	X	X	X
Physicians' assessment According to SMF	X		X	X	X	X	X
Adverse Events	X	X	X	X	X	X	X

Section 1: Administrative information

Title and Trial registration

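### No written step requires a check of recent anticoagulant/NSAID use or pregnancy before re-injection, and the NSAID comfort advice has no timing limit

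*Protocol*

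**What the plan says.** The Protocol's Exclusion Criteria, repeated in the SAP, bar "Those using anticoagulants or NSAID or other medications that increase the risk of coagulation disorders within 7 days before injection" and "Pregnant or lactating women". The drug exclusion is tied to injection and does not single out the first. The Intervention section allows one to three sessions "with at least 4 weeks intervals". Withdrawal of Subjects, in both documents, lists meeting any exclusion criterion during the study as a reason for withdrawal.

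The check itself appears under Visit 0 of Study Visits: "The investigator will evaluate each patient against the inclusion and exclusion criteria". The Study Timeline agrees. Its eligibility row reads "eligibility control | X", with no later mark, and the SAP's Participate timeline has the same "eligibility control" row. By contrast, the injection row is "Injection | | X | X | X" and the adverse-event row is "Adverse Events | X | X | X | X | X | X | X".

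The Protocol gives comfort advice twice. The line under Intervention names cold packs and local anaesthesia. The line under Warnings and Precautions adds NSAIDs and does not say when they may be taken.

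**The concern.** Recent drug use and pregnancy can both change between visits. Someone clear of both at Visit 0 may have taken an NSAID in the week before Visit 2, or become pregnant before Visit 3. If the rule holds at every injection but the only written check is at entry, a site can follow the schedule exactly and still give an injection that the protocol bars.

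The stake is subject safety. Bruising is listed among the very common reactions and bleeding among the common ones, and safety is part of the primary objective. The untimed comfort advice adds a route to the barred exposure, because a subject or site could read it as allowing an NSAID before a session.

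**Working it through.** The plan states no figure on this point, so there is none to reproduce. The check compares the rule with the schedule and then does day arithmetic.

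**1. Does the rule bind at re-injection?** The exclusion list does not say *every* injection. Two texts together lead there: the drug window is set relative to injection in a regimen of up to three, and the withdrawal rule keeps all exclusion criteria in force after entry. For pregnancy and lactation, the withdrawal rule alone is enough.

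**2. Can a Visit 0 check cover the later windows?** Inputs from Study Visits: Visit 2 at 4 weeks ± 2 days, Visit 3 at 8 weeks ± 4 days. Days are counted from injection 1.

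- Injection 2: 28 ± 2 = days 26 to 30. The 7-day window opens on day 26 − 7 = 19 to day 30 − 7 = 23.
- Injection 3: 56 ± 4 = days 52 to 60. The window opens on day 52 − 7 = 45 to day 60 − 7 = 53.
- If the 4-week minimum interval is kept, the earliest injections are days 28 and 56, and the windows open no earlier than days 21 and 49.

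Visit 0 falls on or before the day of injection 1, so it covers no part of either window.

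**3. How many injections lack a scheduled check?** At most 2 of 3 per subject. With 20 subjects the ceiling is 20 × 2 = 40 of 20 × 3 = 60 possible sessions. This counts sessions without a written check, not barred injections.

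**4. Does another written step fill the gap?**

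- Physician evaluation 4 weeks after injections 1 and 2 (Intervention): its stated purpose is to decide whether more treatment is needed.
- Palpation before each session (Method of administration): looks for sufficient fat and the correct tissue layer.
- Adverse-event causality grading: asks whether other drugs could explain an event. It does not ask about the 7 days before the coming injection, and it does not cover pregnancy.
- Timeline rows: none for concomitant medication or pregnancy at any visit.

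Each of the first three is an occasion on which someone might ask. None requires the question or a record of the answer.

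**5. Is the NSAID advice in conflict with the exclusion?** Use soon after an injection is compatible: at the minimum interval, 28 − 7 = 21 days remain before the next window opens. Use before a session, or in the last 7 days before the next one, is not. The Warnings line does not separate these cases.

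**The case against.** The best reply is that a single mark in the eligibility row proves little. Eligibility control sits with screening, consent and demographics as an entry step, and the timeline omits other recurring duties: palpation and the half-hour observation have no row. That stands, so the point cannot rest on the row alone. It rests on there being no such step in the timeline, the visit descriptions, the Intervention section or the administration instructions. The Visit 2 and 3 lists are abbreviated and carry no weight by themselves.

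A reader might infer that nobody is asked to attend to these criteria after entry. The documents do not support that. The withdrawal rule creates a standing duty, a physician must evaluate each subject before further treatment, and causality grading often calls for medication information. The separately approved CRF is not available here and may contain the questions. What remains is that the protocol and SAP do not write the check down.

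A reader might also infer that the NSAID advice flatly contradicts the exclusion. It does not. It can be read as advice for after injection, and the specific 7-day rule can be taken to limit it. The conflict arises only for use before a session, but nothing in the line excludes that use.

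**Conclusion.** The point holds as a cheap patient-safety improvement. Evaluation against the exclusion criteria is scheduled at Visit 0 only. The drug and pregnancy or lactation exclusions still apply at Visits 2 and 3, and no written step requires them to be checked before re-injection. The untimed NSAID line needs a limit.

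This rests on reading the drug exclusion as applying to each injection, which the withdrawal rule supports, and on the protocol and SAP text alone.

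The size is one scheduled check for up to three injections per subject. The documents give no rate of drug use or pregnancy, so the frequency of barred injections cannot be estimated, and it would be wrong to infer that they are common. Nor does the gap undermine the efficacy results: no endpoint, sample size or analysis figure changes.

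**What to change.** **(a) Pre-injection check.** Add a row to the timeline in both documents, marked at Visits 2 and 3, and a line to the re-injection lists for those visits. Mark it at Visit 1 too if that is not the same day as Visit 0. Suggested wording: *Before injection, ask and record: any anticoagulant, NSAID or other coagulation-affecting drug in the previous 7 days; pregnancy or lactation. If yes, withhold this injection.*

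State what follows a yes at Visit 2 or 3:

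- A pregnant or lactating subject receives no further injections.
- A subject barred only by recent drug use is not injected at that visit.
- Both stay in post-injection follow-up for safety and outcome data and are not dropped.

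The last item needs a matching sentence in Withdrawal of Subjects. Read literally, the present rule could remove a subject for one NSAID dose, which is 1 of 20 = 5% of the sample, and the SAP plans no imputation.

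The existing visits accommodate this. Follow-up runs 4 and 12 weeks after the last injection given: weeks 0 + 4 = 4 and 0 + 12 = 12 after one injection, and weeks 4 + 4 = 8 and 4 + 12 = 16 after two. No delay rule is needed. If the sponsor prefers one, later visits must move: injection 2 on day 35 puts injection 3 no earlier than 35 + 28 = day 63, which is 3 days past the end of the Visit 3 window (day 60).

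**(b) Comfort advice.** Limit the Warnings line to: *NSAIDs after injection only, and none within 7 days before the next planned injection.* At least 21 of the 28 days between sessions remain open for such use.

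**Cost.** One timeline row in each document, a line in two visit lists, a sentence in the withdrawal section of each document and one edited sentence in the Warnings. In practice this means a few minutes per visit and an occasional injection not given. No extra visit, staff or procedure is needed.

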- The product is a 2 ml sterile, transparent, and colorless vial containing 20 mg of DCA. Additional ingredients include hyaluronic acid, water for injection, sodium chloride, sodium hydroxide, hydrochloric acid, and disodium phosphate anhydrous.
- Use of ice/cold packs, topical and/or injectable local anesthesia (e.g., lidocaine) may enhance patient comfort.

Method of administration

The product is indicated for subcutaneous administration only.

[figure not shown]
EMBELLA® is supplied in ready-to-use, single-use vials. Gently invert the vial several times before use. Do not dilute.

EMBELLA® shall be prepared for injections in the following way:

1. Remove the flip-off cap from the vial and clean the penetrable stopper of the vial with an antiseptic. If the vial, seal, or flip-off cap is damaged, do not use it.
2. Attach a large bore sterile needle to a sterile single-use 1 ml syringe.
3. Introduce the large bore sterile needle into the stopper of the vial and draw 1ml of EMBELLA® into the 1ml syringe.
4. Replace the large bore needle with a 30 gauge (or smaller)-0.5-inch needle. Expel any air bubbles in the syringe barrel before injecting the product into the subcutaneous fat.
5. To withdraw the remaining contents of the vial, repeat steps 3 and 4.

[figure not shown]
For injection, the needle is inserted perpendicular to the skin, and injection should be avoided in the area defined by a line 1 to 1.5 cm from the angle of the mandible to the mentum (Figure 1).

Figure 1. Avoid the Marginal Mandibular Nerve Area

[figure not shown]
Avoid injection into the platysma. Prior to each treatment session, palpate the submental area to ensure sufficient submental fat and to identify subcutaneous fat between the dermis and platysma (pre-platysmal fat) within the target treatment area (Figure 2).

Figure 2. Sagittal View of Platysma Area

Outline the planned treatment area with a surgical pen and apply a 1 cm^2 injection grid to mark the injection sites (Figures 3).

Figure 3. Injection Pattern

WARNINGS AND PRECAUTIONS

- Embella[®] should only be injected within the defined parameters. Each vial is intended for use in one patient and should be discarded after use.
- Store the product between 15°C and 30°C.
- Use of ice/cold packs, topical and/or injectable local anesthesia, and NSAIDs may enhance patient comfort.

[figure not shown]
[figure not shown]
[figure not shown]
[figure not shown]
[figure not shown]
[figure not shown]
[figure not shown]
Endpoints

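### For subjects who stop after one or two injections, the 4-week primary SMF grade comes from the response-dependent stopping visit, and the plan does not say whether the 4-week or the 12-week result leads.

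*Protocol*

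**What the plan says.** The primary endpoint (Protocol, Primary Endpoint; SAP Section 4) is "At least one-grade improvement in standard grading of submental fat (SMF) evaluated at 4 and 12 weeks after the last injection". Neither document puts one time first or says whether response is needed at one or both. SAP Section 5 compares each parameter among visits with a paired t-test or Wilcoxon test at p < 0.05.

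Whether an injection is the last is settled during treatment. Protocol, Intervention: "4 weeks after the first and second injections, the patient will be evaluated by the physician and research team", and then "If necessary, they will receive additional injections; otherwise, they will proceed with post-injection follow-up". The Study Timeline describes those who stop at Visit 2 or 3 under "Follow-up of subjects with a satisfactory response who do not require further treatment". The Study Visits section uses "In case of complete recovery with the physician's opinion" for the same branch.

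The grade is listed in the timeline as "Physicians' assessment According to SMF", and no masked or independent grader is described. The design is a single group of 20 without a control.

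**The concern.** Timing the endpoint from the last injection makes the 4-week reading depend on the decision to stop. A subject who looks good enough at Visit 2 or 3 stops, and that visit's grade becomes the 4-week primary value. A subject who does not is re-injected, and the 4-week reading moves to a later visit. If the decision follows what is graded, a reading that is favourable by error is kept, while an unfavourable one is replaced by a new reading. The same applies to a change that does not last.

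With 20 subjects and no control group, nothing in the data would show how much of the 4-week result comes from this. Because no time leads, the higher result can carry the conclusion. A fall from 4 to 12 weeks can also be read as loss of effect when part of it is selection.

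**Working it through.** **Visit mapping (from the timeline).**

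| Injections | 4-week grade | 12-week grade | Is the 4-week visit a stopping visit? |
|---|---|---|---|
| 1 | Visit 2 (week 4) | Visit 4 (week 12) | Yes |
| 2 | Visit 3 (week 8) | Visit 5 (week 16) | Yes |
| 3 | Visit 4 (week 12) | Visit 6 (week 20) | No |

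No 12-week grade is a stopping reading. This step needs no assumption.

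**Plan figure.** The sample size of 20 comes with no response rate, power or grading reliability, so there is nothing to reproduce. The argument does not depend on it.

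**Assumptions for size (none is in the documents).** Each reading is one grade too low with probability q, one too high with probability q, and otherwise correct, within the 0–4 scale. Errors are independent and true grades 1–4 are equally likely. There are up to three readings; the first to meet the stop rule, or else the third, is the 4-week value. A later independent reading is the 12-week value. Stop rules, closest to complete recovery first:
- C: grade 0.
- B: a gain that reaches grade 0 or 1.
- A: any one-grade gain.
- D: unrelated to the grade.

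**No true effect, q = 10%, by hand.**

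*12 weeks, any rule.* True grade 1–3: (1−2q)q + q(1−q) = 0.08 + 0.09 = 0.17. True grade 4: (1−q)q = 0.09. Mean: (3 × 0.17 + 0.09)/4 = 15.0%.

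*4 weeks.* The chance that at least one of three readings is low is 1 − 0.9³ = 0.271.
- A: true 1–3, 0.8 × 0.271 + 0.1 × (1 − 0.1³) = 0.3167; true 4, 0.9 × 0.271 = 0.2439. Mean: (3 × 0.3167 + 0.2439)/4 = 29.9%.
- B: true 1, 0.3167; true 2, 0.8 × 0.271 + 0.1 × (1 − 0.9² × 0.1) = 0.3087; true 3, 0.17; true 4, 0.09. Mean: 0.8854/4 = 22.1%.
- C: only true grade 1 can be misread as 0, giving 0.3087; the others stay at 0.17, 0.17 and 0.09. Mean: 0.7387/4 = 18.5%. If all true grades are 2–3, the gap is zero.
- D: 15.0%.

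Simulation agrees, and gives for q = 5/10/15%:

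| Rule | 4 weeks, % | 12 weeks, % | Gap, points |
|---|---|---|---|
| C | 10/18/25 | 8/15/21 | 2/3/4 |
| B | 12/22/30 | 8/15/21 | 4/7/9 |
| A | 17/30/40 | 8/15/21 | 9/15/19 |
| D | 8/15/21 | 8/15/21 | 0 |

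**Planned test, no true effect.** Shapiro-Wilk rejects normality of the grade changes in 96.7–100% of simulated trials, so the SAP leads to Wilcoxon. It declares improvement at 4 weeks in about 3–5% of trials under C, 5–8% under B and 10–21% under A, against a nominal 2.5%. At 12 weeks it does so in about 1.5–2.5%.

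**Real, lasting effect** (40% chance of a one-grade drop per injection, q = 10%; true/4-week/12-week response, %):

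| Rule | All subjects | Early stoppers only | Share stopping early, % |
|---|---|---|---|
| C | 77/75/71 | 90/93/78 | 23 |
| B | 75/76/70 | 86/100/83 | 38 |
| A | 71/79/66 | 82/100/81 | 66 |

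Without misreading both times agree, at 78%.

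**Carry-over.** If 25–50% of 12-week grades simply repeat the 4-week grade (no effect, q = 10%), the 12-week rate rises from 15% to about 16–17% (C), 17–19% (B) or 19–22.5% (A).

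**Second error model.** With a continuous latent grade and reading-error SD of 0.25–0.55 grade, the gap runs from about 2 to 23 points depending on rule, error and effect. It is zero without reading error or when stopping is unrelated to response.

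**The case against.** **The grade is not the stop criterion.** This stands. The physician and research team evaluate the subject, "Prior to each treatment session, palpate the submental area to ensure sufficient submental fat" is a further input, and the visit text lists grading after the recovery opinion. Rule A also fits complete recovery poorly, since a change from grade 4 to 3 would count. Under C the gap is 2–4 points, less than one subject in 20 (20 × 0.04 = 0.8). But the timeline uses the looser wording, and both wordings describe the same submental fat that is graded at that visit.

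**With a real effect, 12 weeks is not nearer the truth.** This stands for C and B: at q = 10% the 4-week rate lies closer to the true rate, because ordinary misreading lowers the 12-week rate. Only under A does the 4-week rate clearly exceed the truth. The case for 12 weeks is that it is not the stopping reading and does not inflate false positives, not that it is unbiased.

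**Misreading may be rarer.** The Protocol Introduction reports no improvement on placebo in the cited trial. At q = 1–2% with a real effect, the 4-week rate differs from the truth by under 1 point under C and B and by at most about 2 under A. The size shrinks; the mechanism remains.

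**Both times are prespecified and will be reported, with no success threshold.** True, and it limits the harm. It does not say which result carries the conclusion.

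**Changing the primary time may be outcome switching.** The protocol is partly in the past tense, so results may exist. The change would then have to be declared.

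**Conclusion.** The concern holds as a design weakness of moderate weight that is cheap to correct. The documents alone establish three things: the 4-week primary grade of one- and two-injection subjects is taken at the stopping visit, stopping depends on response, and neither primary time leads. Three-injection subjects are unaffected.

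Upward selection is possible but not proven. It requires that the decision follows the graded appearance, and that grading errs or the change does not last. Under the assumptions above with no true effect, the gap between the two times is 2–4 points on the strict reading of the stop condition, 9–19 on the loosest, and zero if stopping is unrelated to the grade. With a real effect, the distortion is seen mainly among early stoppers, and overall only on the loosest reading. The 12-week grade is much less exposed, but not immune if grading error or assessor expectation carries over. Confidence in the size is medium at best.

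**What to change.** 1. In Protocol, Primary Endpoint, and SAP Section 4, name one primary endpoint: the proportion of subjects whose SMF grade is at least one lower than at baseline 12 weeks after the last injection (Visit 4, 5 or 6 for one, two or three injections).
2. Make the 4-week grade (Visit 2, 3 or 4) a descriptive secondary endpoint, reported by number of injections. State that for one or two injections it was taken at the re-injection decision visit. Keep these split rates descriptive: they are selected through the shared baseline grade. Under rule A with no effect and q = 10%, three-injection subjects show 8.8% at both times, against 15% at 12 weeks overall.
3. Separately, and not as support for the bias argument, reconcile the differing wordings of the stop condition (Intervention, Study Timeline, Study Visits). Also reconcile the listing of SMF grading at Visits 2 and 3: the timeline marks it for everyone, while the branch headed "If re-injection is needed" omits it. No stop rule is proposed here.

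The cost is text edits in two documents, with no added visit, subject or delay, because the 12-week reading is already primary and scheduled. It also leaves one primary test at 0.05 in place of two unadjusted ones. The downsides are that the 4-week reading loses primary status and that slightly more data may be missing at 12 weeks, with no imputation planned. If results have been seen, declare the change as post hoc and keep reporting both times.
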